### **6.4.3 Prohibited concomitant therapy**

During the course of the study, patients may not receive other additional investigational drugs, agents, devices, chemotherapy, or any other therapies that may be active against cancer. However, limited-field palliative radiotherapy to non-target lesion(s) may be allowed as concomitant therapy after documented discussion with Novartis. For patients with anaplastic thyroid cancer, limited-field radiotherapy to a target lesion that is life-threatening may be allowed, provided that other measurable disease remains to allow an assessment of response to treatment. These cases must be discussed with Novartis with written permission. Such local therapies administered during the study treatment must be listed on the Concomitant Antineoplastic Therapy – Radiotherapy CRF.

After progression of disease as per RECIST criteria, radiotherapy and surgery to select target and non-target lesion(s) (such as brain metastases) may be allowed as concomitant therapy after documented discussion and approval by Novartis.

Additionally, no other therapeutic monoclonal antibodies and no immunosuppressive medication may be administered while on this study.

The use of systemic steroid therapy is not allowed, except for the treatment of the following: infusion reactions, immune-mediated toxicities (patients may resume study treatment while on tapering with doses  $\leq$  10 mg/day prednisone or equivalent), COPD exacerbation and replacement-dose steroids in the setting of adrenal insufficiency. Additional exceptions may be discussed with Novartis. Topical, inhaled, nasal and ophthalmic steroids are not prohibited.

The use of live vaccines is not allowed through the whole duration of the study.

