### 7.1.3 Treatment period

A treatment cycle is defined as 28 days for the Q2W and Q4W regimens and 21 days for the Q3W regimen, for the purposes of scheduling procedures and evaluations. Please refer to Table 7-1 for details of the timing of required assessments and Section 7.1 for visit windows.

Patients will be treated until they experience unacceptable toxicity, progressive disease per irRC and/or treatment is discontinued at the discretion of the investigator or the patient, as described in Section 7.1.4 and Section 4.3. Patients should not discontinue treatment based on progressive disease per RECIST.

Patients who have disease progression and have evidence of clinical benefit, such as disease shrinkage at other sites or symptomatic improvement, may continue treatment with PDR001. In addition, PDR001 treatment may be temporarily interrupted to permit local therapy for symptomatic metastases after disease progression has been documented. Patients who continue on treatment after disease progression should discontinue study treatment once they are no longer deriving benefit as assessed by the investigator.

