### **10.5.2 Other secondary efficacy objectives**

Tumor response will be determined per local investigators' assessment. Secondary efficacy endpoints will include BOR, ORR, PFS, DCR and DOR for Phase I and Phase II. In Phase II, BOR and ORR will be defined and analyzed based on tumor assessment by irRC as described in [Appendix 14.2](#) only. PFS, DCR and DOR for Phase II and all secondary efficacy endpoints for Phase I will be defined and analyzed based on tumor assessment by RECIST 1.1 and irRC as described in [Appendix 14.1](#) and [Appendix 14.2](#), respectively.

Definitions for these endpoints according to RECIST 1.1 are provided in [Appendix 14.1](#). Definitions accordingly to irRC are similar to these for RECIST 1.1 and are provided in the RAP.

For irRC the key difference from RECIST in the assessments of these endpoints is the requirement for confirmation of PD not less than 4 weeks after the criteria for PD are first met. The date of the first of these two assessments is then the date of confirmed progression. For

patients who have ended treatment without a valid confirmation assessment, for the purposes of analysis the single assessment of PD will be treated as a confirmed PD. A single assessment of PD followed by a subsequent assessment of SD or better will be considered as a pseudo-progression, and will not be used for analysis.

Individual lesion measurements and overall response assessments will be listed by patient and assessment date. BOR, PFS, DCR and DOR will be listed by patient.

The following analyses will be presented by treatment group for patients treated in the phase II part.

- BOR will be summarized
- ORR (irRC) and DCR will be summarized with an accompanying [90%] exact binomial confidence interval (CI).
- For PFS the survival function will be estimated using the Kaplan-Meier (KM) product limit method and displayed graphically. Median duration, with a two-sided 90% CI, and 25th and 75th percentiles (Brookmeyer 1982, Klein 1997) will be presented. KM estimates of survival proportions at specified time points, along with corresponding 90% CIs (Greenwood's formula, Kalbfleisch 1980) will also be provided.

For DOR, KM estimates may be provided if sufficient numbers of patients respond.

BOR will be listed and summarized, and ORR and DCR will be summarized with an accompanying 90% exact binomial CI by treatment group for all patients treated in the phase I part.

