Per irRC, irCR, irPR and irPD need to be confirmed with at least two determinations of irCR or irPR or irPD, respectively at least 4 weeks apart. In order to classify overall response as irSD, the patient must have at least one SD assessment (or better) > 6 weeks after start date of study treatment.

Individual lesion measurements and overall response assessments will be listed by patient and assessment date. Best overall response (BOR) per RECIST v1.1 and per irRC will be listed and tabulated.

Overall response rate (ORR) and Disease control rate (DCR)

ORR is the proportion of patients with a best overall response of CR or PR (RECIST v1.1) or of irCR or irPR (irRC). DCR is the proportion of patients with a best overall response of CR, PR, or SD (RECIST v1.1) or of irCR, irPR, or irSD (irRC).

Progression free survival (PFS)

For assessment per RECIST v1.1, PFS is the time from date of start of treatment to the date of event defined as the first documented progression or death due to any cause. If a patient has not had an event, PFS is censored at the date of last adequate tumor assessment ([CPDR001X2101 Amendment 8 Appendix 14.1.3.2.1]). For irRC, PFS is defined similarly, but with the date of event defined as the date of the first documented confirmed progression as defined in Section 4.2.3, or death due to any cause. For irRC, other censoring rules are applied as for RECIST v1.1 ([CPDR001X2101 Amendment 8 Appendix 14.1.3.2.9]).

Duration of response (DOR)

DOR applies only to patients with a BOR of confirmed CR or PR (RECIST v1.1) or of confirmed irCR or irPR (irRC). For assessment per RECIST v1.1, DOR is defined as the time from the date of the first documented response (CR or PR) to the date of first documented progression, or death due to any cause. For assessment per irRC, DOR is defined as the time from the first confirmed response (irCR or irPR), to the date of confirmed progression as defined in Section 4.2.3, or death due to any cause.

Use of alternative cancer therapy

For both RECIST v1.1 and irRC, if any alternative cancer therapy is taken other than palliative radiotherapy any subsequent assessments will be excluded from the analysis of endpoints based on tumor response assessments. If a substantial number of patients receive palliative radiotherapy, sensitivity analyses of these endpoints may be performed where assessments are also censored at the time of palliative radiotherapy.

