4.2.2.1 Pseudo-progression

Subjects with a single irPD, followed by an assessment of irSD or better will be considered to have a pseudo-progression (pPD). For the purposes of analysis, pseudo-progressions are not treated as progression events.

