4.2.3 Best overall response

Assessment of BOR will be based on all assessments up to and including the first assessment of irPD (cPD1, cPD2, or uPD). Assessments made after start of new anti-cancer therapy, will be excluded.

BOR will be defined with the following hierarchy:

irCR	Two consecutive determinations of irCR ≥28 days (4 weeks) apart
	Non-consecutive assessments of irCR may also result in BOR of irCR if all intervening assessments are irUNK
irPR	•
IIPK	Two determinations of irPR (or better) \geq 28 days (4 weeks) apart
	The two determinations of irPR (or better) may be separated by one or more
	assessments of irSD, but may not be separated by an assessment of irPD
irSD	At least one irSD assessment (or better) > 42 days (6 weeks) after first treatment
irPD	Event flagged as cPD1, cPD2 or uPD ≤ 84 days (12 weeks) after first treatment
irUNK	All other cases

4.2.4 Time to event analyses:

4.2.4.1 **Progression events**

PDs flagged as pPD are not included in time to event analyses.

SAP final CSR 24-Jul-2020 (11:48) CPDR001X2101

Subjects are classified as follows:

	0	No event (censored) Confirmed PD (cPD1 or cPD2)	
	1		
Ī	2	Unconfirmed PD (uPD)	

For the primary analysis of time to event endpoints, both confirmed and unconfirmed progression will be included as progression events with date of progression being the date of the assessment flagged as cPD1, cPD2 or uPD according to the algorithm defined in Section 4.2.2.

A sensitivity analysis of time to event endpoints may be conducted in which subjects with unconfirmed PD are treated as censored, with date of last adequate assessment = visit date for assessment flagged uPD.

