4.2.4.4 Duration of response

Duration of response is defined as a time interval between the first date of confirmed PR/CR and the date of progression as defined in Section 4.2.4.1, or death due to any cause. Intervening assessments of pPD are excluded from the assessment.

Date of confirmed response

Response (irPR or irCR) should be confirmed by a second assessment no less than 4 weeks after the first assessment showing response. Date of response is then the date of the first of these two assessments. For confirmation of irCR the two assessments must be consecutive (intervening assessments of irUNK are permissible). For confirmation of irPR the two assessments do not need to be consecutive, but must not be separated by a pseudo-progression event.

The table below shows a hypothetical data scenarios with programming instructions.

Sequence of assessments	Instructions	
1 irPR	The first PR (assessment 1) is followed by a pseudo-progression	
2 irPD	(assessment 2) and is therefore not confirmed	
3 irPR	Subsequently the Subject has a irPR (assessment 3) which is	
4 irPR	confirmed at the following assessment (assessment 4)	
	The BOR for this Subject is irPR, with date of confirmed irPR equal to the date of assessment 3	

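### SAP 4.2.2.1 lets a scan made after palliative radiotherapy reclassify an irPD as pseudo-progression, which can delay or censor irRC PFS and DOR events

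*SAP*

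**What the plan says.** **Classification.** SAP 4.2.2.1: "Subjects with a single irPD, followed by an assessment of irSD or better will be considered to have a pseudo-progression (pPD". Protocol 10.5.2 has the same rule: "A single assessment of PD followed by a subsequent assessment of SD or better will be considered as a pseudo-progression". Neither text asks whether a lesion was treated locally between the two scans.

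**Consequence.** SAP 4.2.2.1: "For the purposes of analysis, pseudo-progressions are not treated as progression events". SAP 4.2.4.1: "PDs flagged as pPD are not included in time to event analyses". For duration of response, SAP 4.2.4.4: "Intervening assessments of pPD are excluded from the assessment".

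**Local therapy.** Once a patient has progressed by RECIST, Protocol 6.4.3 provides that "radiotherapy and surgery to select target and non-target lesion(s) (such as brain metastases) may be allowed as concomitant therapy", subject to documented sponsor approval. Protocol 7.1.3 adds: "PDR001 treatment may be temporarily interrupted to permit local therapy for symptomatic metastases after disease progression has been documented".

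**Scans after other therapy.** SAP 3.4, under use of alternative cancer therapy: "if any alternative cancer therapy is taken other than palliative radiotherapy any subsequent assessments will be excluded from the analysis". Scans after palliative radiotherapy therefore stay in. The next sentence of SAP 3.4 offers a sensitivity analysis that censors at palliative radiotherapy, but only as an option and only if a substantial number of patients receive it. No threshold is given.

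**The concern.** The pseudo-progression rule reads a later irSD or better as evidence that the first irPD was not true progression. That inference is sound only if nothing other than the study drug changed the measured burden in between. Radiotherapy to the lesion that grew is another explanation for the better scan, and the rule does not separate the two.

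The protocol is careful about irradiated disease elsewhere. Exclusion criterion 19 requires phase II patients to have remaining measurable disease that has not been irradiated. Section 6.4.3 attaches a similar condition to target-lesion radiotherapy in anaplastic thyroid cancer. Section 10.4.4 plans ORR sensitivity analyses censored at palliative radiotherapy if enough patients receive it. The pseudo-progression rule has no such protection.

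At stake is the date, and sometimes the presence, of an irRC progression event. Where the rule operates, irRC PFS and DOR are lengthened by the local treatment. The undefined term palliative also means that two programmers could derive different irRC PFS from the same data.

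**Working it through.** The plan states no event count, rate or power for irRC PFS or DOR, so there is no figure to reproduce. The check traces the rule on constructed patients and then gauges size under stated assumptions.

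**Inputs from the documents**
- irPD: sum of diameters, new measurable lesions included, at least 20% and at least 5 mm above nadir (Protocol 14.2.4).
- irSD: neither irPR nor irPD. With target burden below +20% and non-target lesions absent, stable or not evaluated, the reading is irSD (Protocol Table 14-6).
- Flags cPD1, cPD2, uPD and pPD: SAP 4.2.2. The first three are events in the main analysis (SAP 4.2.4.1).
- Scans every 8 weeks up to week 40 (Protocol 7.2.1).

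**Step 1: one irradiated lesion (constructed)**
- Nadir: A 20 mm + B 50 mm = 70 mm.
- Week 16: A 38 mm, sum 88 mm. Change (88 − 70)/70 = +25.7% and +18 mm, so irPD.
- A is irradiated. Week 24: A 18 mm, sum 68 mm. Change (68 − 70)/70 = −2.9%, so irSD, or irPR if the baseline sum was at least 68/0.7 = 97.1 mm.
- Either reading makes week 16 a pPD, although B did not change.

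**Step 2: what happens to the event date (constructed)**

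Baseline 100 mm, nadir 80 mm, scans on days 56, 112, 168, 224 and 280. The irPD limit is 1.2 × 80 = 96 mm.

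| Course | Sums (mm) | Flag and event date |
|---|---|---|
| No radiotherapy | 85, 80, 100, 112, 125 | cPD1, day 168 |
| Radiotherapy after day 168 | 85, 80, 100, 92, 90 | pPD only, no event |
| Radiotherapy, then regrowth | 85, 80, 100, 92, 112 | uPD, day 280 |
| Post-radiotherapy scans not used | 85, 80, 100 | uPD (cPD2 if off treatment), day 168 |

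The delay in the third row is 280 − 168 = 112 days. A fall from 100 mm to just under 96 mm is enough to reverse the irPD.

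**Step 3: non-target progression**

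If the irPD came from unequivocal non-target progression and target burden is below +20%, no target shrinkage is needed. Under Table 14-6 it is enough that the irradiated non-target lesion is next read as stable or is not evaluated.

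**Step 4: size under assumptions**

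The documents give no radiotherapy rate. All inputs here are assumed: exponential irRC PFS with true median 4.0 months; each converted patient gains 1 month plus an exponential time with median 2 to 4 months; 400,000 simulated patients.

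| Converted | Median PFS (months) | 6-month PFS |
|---|---|---|
| 0% | 4.0 | 35% |
| 2% | 4.1 | 36% |
| 5% | 4.2 | 37–38% |
| 10% | 4.4–4.5 | 38–40% |
| 20% | 4.8–5.1 | 42–44% |

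In a group of 60, one converted patient is 1/60 = 1.7%.

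**The case against.** The other side has several good points.

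- **The issue is partly handled.** Censoring at palliative radiotherapy drops the later irSD scan and leaves the irPD as uPD or cPD2. This stands, but the analysis is optional and its trigger undefined.
- **Palliative may not cover this radiotherapy.** Protocol 6.4.3 uses the word for limited-field treatment of non-target lesions and does not use it for radiotherapy after RECIST progression. On that reading SAP 3.4 excludes the later scans and the irPD remains an event. Protocol 10.4.4, however, speaks of palliative radiotherapy to target lesions. The text is ambiguous, so the concern is conditional.
- **The pathway is narrow.** The permission follows RECIST progression, which is not always irPD, because under irRC a new lesion is not automatically progression. If the confirmatory scan comes before radiotherapy and still shows irPD, the event is cPD1. The whole burden must also read irSD or better.
- **A broad fix would bias the other way.** Barring reclassification after radiotherapy to any lesion would turn genuine pseudo-progressions into events when an unrelated painful site was treated. This stands and limits the fix.

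A reader might also infer four stronger things that the documents do not support:
- **Progressions are erased for good.** Only the pPD is dropped; a later irPD or death still counts.
- **Surgery opens the same gap.** Protocol 14.1.3.2.7 counts surgery as secondary anti-cancer therapy, and SAP 3.4 exempts only palliative radiotherapy.
- **A later response would be credited.** The best-overall-response rules in SAP 3.4 and 4.2.3 exclude scans after other anti-cancer therapy and write no radiotherapy exemption.
- **A RECIST-to-irRC gap in PFS would be read as delayed immune benefit.** No such comparison is planned.

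**Conclusion.** The concern holds in a conditional form. If radiotherapy after RECIST progression counts as palliative, the rule as written can turn a true irPD into a pseudo-progression because an irradiated lesion shrank or was no longer read as progressing. The irRC PFS or DOR event is then delayed to the next irPD or death, or censored if neither follows.

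The size cannot be determined from the documents. The simulated shifts, about 0.1 to 0.2 months in the median at 2% to 5% conversion, rest wholly on assumed inputs. Exposure is confined to secondary irRC time-to-event endpoints. RECIST PFS and DOR use the first documented progression, and the primary phase II endpoint, RECIST ORR, does not use the pseudo-progression rule. The point still merits correction, because a rule followed exactly can misdate a true progression and the remedy is small.

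**What to change.** 1. Add to SAP 4.2.2.1 that an irPD is not reclassified as pPD on the basis of a scan made after radiotherapy to a lesion that contributed to that irPD. Keep it as an event at the irPD date, handled like cPD2 or uPD. Limiting the condition to contributing lesions protects genuine pseudo-progressions.
2. State in SAP 3.4 whether radiotherapy given after RECIST progression counts as palliative, and align that paragraph with the best-overall-response rules in SAP 3.4 and 4.2.3.
3. Report the number of pPD with and without intervening radiotherapy, and run the sensitivity analysis censoring at radiotherapy whenever at least one such case occurs.

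**Cost.** One derivation condition, one definition, one count and one firm sensitivity analysis, made by SAP amendment or, after database lock, by addendum (SAP 1). Concomitant antineoplastic radiotherapy is already collected (Protocol 6.4.3 and Table 7-1). The documents do not show whether that form identifies the lesion, so matching may need a review of irradiated sites against the lesion listing. irRC PFS and DOR may become slightly less favourable. No clinical rule changes.

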4.2.2.2 Confirmed progression

Confirmed progression 1 (type 1, cPD1) is declared if a subject has 2 consecutive tumor assessments at least 4 weeks (28 days) apart both showing disease progression. Assessments with an UNK response or PD assessments < 28 days after initial PD, are discarded.

The first PD is flagged as cPD1 while all subsequent PDs are flagged as xPD1.

The table below shows two hypothetical data scenarios and programming instructions.

Sequence of assessments	Instructions
1 irPD 2 irUNK	 Assessment 3 is ≥28 days after Assessment 1 Assessment 3 represents confirmation of irPD at
3 irPD (Assessment 1 + 30 days)	assessment 1
	Assessment 1 irPD is flagged cPD1
	Assessment 3 irPD is flagged xPD1
1 irSD	Assessment 3 is < 28 days after Assessment 2
2 irPD	 Assessment 4 is ≥ 28 days after Assessment 2
3 irPD (Assessment 2 + 20 days)	Assessment 4 represents confirmation of irPD at
4 irPD (Assessment 2 + 30 days)	assessment 2
	Assessment 2 irPD is flagged cPD1
	 Assessment 3 and 4 irPDs are flagged xPD1

Confirmed progression 2 (type 2, cPD2) is declared if a subject discontinues treatment following a single PD with no subsequent assessments ≥ 28 days later. Assessments with an UNK response or PD assessments < 4 weeks (28 days) after initial PD, are discarded. Discontinuation of treatment is obtained from EOT case report form.

The assessment is flagged as cPD2 and subsequent PDs (<28 days after first PD) are flagged as xPD2.

The table below shows two hypothetical data scenarios and programming instructions.

Sequence of assessments	Instructions
1 irSD	Subject withdraws after initial progression (Assessment 2) without
2 irPD	confirmation
- EOT	Assessment 2 irPD is flagged as cPD2
1 irPD	Assessment 2 irPD is <28 days after Assessment 1, so does not
2 irPD (Assessment 1 + 20 days)	represent confirmation
- EOT	However, subject has completed treatment
	Assessment 1 irPD is flagged cPD2
	Assessment 2 irPD is flagged xPD2

4.2.2.3 Unconfirmed progression

Subjects with a single irPD, and no assessment of irSD or better (assessment with an irUNK response or irPD assessments < 4 weeks after initial irPD, are discarded) continuing treatment at the time of the analysis will be considered as unconfirmed (uPD).

4.2.3 Best overall response

Assessment of BOR will be based on all assessments up to and including the first assessment of irPD (cPD1, cPD2, or uPD). Assessments made after start of new anti-cancer therapy, will be excluded.

BOR will be defined with the following hierarchy:

irCR	Two consecutive determinations of irCR ≥28 days (4 weeks) apart
	Non-consecutive assessments of irCR may also result in BOR of irCR if all intervening assessments are irUNK
irPR	•
IIPK	Two determinations of irPR (or better) \geq 28 days (4 weeks) apart
	The two determinations of irPR (or better) may be separated by one or more
	assessments of irSD, but may not be separated by an assessment of irPD
irSD	At least one irSD assessment (or better) > 42 days (6 weeks) after first treatment
irPD	Event flagged as cPD1, cPD2 or uPD ≤ 84 days (12 weeks) after first treatment
irUNK	All other cases

4.2.4 Time to event analyses:

4.2.4.1 **Progression events**

PDs flagged as pPD are not included in time to event analyses.

SAP final CSR 24-Jul-2020 (11:48) CPDR001X2101

Subjects are classified as follows:

	0	No event (censored) Confirmed PD (cPD1 or cPD2)	
	1		
Ī	2	Unconfirmed PD (uPD)	

For the primary analysis of time to event endpoints, both confirmed and unconfirmed progression will be included as progression events with date of progression being the date of the assessment flagged as cPD1, cPD2 or uPD according to the algorithm defined in Section 4.2.2.

A sensitivity analysis of time to event endpoints may be conducted in which subjects with unconfirmed PD are treated as censored, with date of last adequate assessment = visit date for assessment flagged uPD.

